6.4. Baseline and Other Summaries and Analyses**6.4.1. Summary of Hemophilia History**

Number and percentage of subjects with Hemophilia A or Hemophilia B, subjects with hemophilic arthropathy, as well as subjects with target joint (s) will be summarized by dose

level and cohort and overall. Historical ABR during the 6 months prior to screening will be summarized descriptively by dose level and cohort.

6.4.2. Study Conduct and Subject Disposition

Subject evaluation groups will show end of study subject disposition and will show which subjects were analyzed for each analysis set. Frequency counts will be supplied for subject discontinuation(s) by dose cohort.

Data will be reported in accordance with the sponsor reporting standards.

6.4.3. Demographic and Clinical Examination Data

A breakdown of demographic data will be provided for age, race, weight, body mass index and height in accordance with the sponsor reporting standards.

6.4.4. Discontinuation(s)

Subject discontinuations, temporary discontinuations or dose reductions due to adverse events will be detailed and summarized by dose cohort.

Data will be reported in accordance with the sponsor reporting standards.

6.4.5. Study Treatment Exposure

Study drug administration will be provided in a listing in accordance with the sponsor reporting standards.

6.4.6. Concomitant Medications and Non-Drug Treatments

All concomitant medication(s) as well as non-drug treatment(s) will be provided in the listings.

6.5. Safety Summaries and Analyses

6.5.1. Adverse Events

Adverse events (AEs) will be reported in accordance with the sponsor reporting standards. AEs will also be summarized separately by inhibitor status, if applicable.

In addition, thrombotic events will be listed and summarized by dose level and cohort if data permits. A list of thrombotic events is provided in Appendix 1 of the protocol. If the subject has received concomitant administration of a bypass agent (ie, NovoSeven, NovoSeven RT, Niasbase, eptacog alfa, FEIBA, Activated prothrombin complex concentrate, APCC, anti-inhibitor coagulant complex concentrate) at the onset of a thrombotic event, the type and dose of bypass agent will be presented as well.

6.5.2. Laboratory Data

Laboratory data (including total globulin, PT/INR, aPTT, fibrinogen, anti-thrombin III and cardiac troponin I) will be listed and summarized by dose level and cohort in accordance with the sponsor reporting standards. Baseline is as defined in Section 3.1.2. In addition, laboratory parameters identified in the appendix 2 of the study protocol will be summarized categorically against criteria specified in that appendix. The respective assessments will take into account whether each subject's baseline test result is within or outside the laboratory

reference range for the particular laboratory parameter. Two sets of summaries will be generated: one for subjects with normal baseline value and one for subjects with abnormal baseline value.

6.5.3. Vital Signs

Absolute values and changes from baseline in supine systolic and diastolic blood pressure and pulse rate will be summarized by dose level and cohort and study day, according to sponsor reporting standards. Tables will be paged by parameter. Baseline is as defined in [Section 3.1.3](#).

The maximum increase from baseline for supine systolic, diastolic blood pressures and pulse rate will be calculated by first subtracting the baseline value from each post-dose measurement to give the change from baseline. The maximum of these values over the respective period will then be selected, except in the case where a subject does not show an increase. In such an instance, the minimum decrease should be taken.

Similarly, the maximum decrease from baseline for supine systolic, diastolic blood pressures and pulse rate will be determined by selecting the minimum value of the changes from baseline. In cases where a subject does not show a decrease, the minimum increase should be taken.

Maximum absolute values and changes from baseline for vital signs will also be summarized descriptively by dose level and cohort using categories as defined in [Appendix 1](#). Numbers and percentages of subjects meeting the categorical criteria will be provided. All planned and unplanned measurements will be counted in these categorical summaries. All values meeting the criteria of potential clinical concern will be listed.

Maximum increases and decreases in vital signs will be summarized by dose level and cohort according to sponsor reporting standards.

6.5.4. Electrocardiogram

Absolute values and changes from baseline in QT, heart rate, QTcF, PR, RR and QRS will be summarized by dose level and cohort and study day using sponsor reporting standards. Tables will be paged by parameter. Baseline is as defined in [Section 3.1.4](#).

The maximum absolute value (post-dose) and the maximum increase from baseline for QT, heart rate, QTcF, PR, and QRS will be determined over all measurements taken post-dose.

The maximum increase from baseline will be calculated by first subtracting the baseline value from each post-dose measurement to give the change from baseline. The maximum of these values over the respective period will then be selected, except in the case where a subject does not show an increase. In such an instance, the minimum decrease should be taken.

Maximum increase from baseline for QT, heart rate, QTcF, PR and QRS will be summarized by dose cohort, according to sponsor reporting standards.

ECG endpoints and changes from baseline (QTcF, PR and QRS) will also be summarized descriptively by dose level and cohort and study day using categories as defined in [Appendix 1](#) (for QTc these correspond to ICH E14).¹ Numbers and percentages of subjects meeting the categorical criteria will be provided. All planned and unplanned measurements will be counted in these categorical summaries. All values meeting the criteria of potential clinical concern will be listed.

Listings of subjects with any single postdose value ≥ 500 msec will also be produced for QTcF.

6.5.5. Physical Examination

Physical exam results will be provided in a data listing in accordance with the sponsor data reporting standard.

6.5.6. Injection and Infusion Site Reactions

The frequency of injection and infusion site reactions will be summarized and listed by dose level and cohort, according to sponsor reporting standards.

6.5.7. Other Safety Data

6.5.7.1. Immunogenicity

The immunogenicity results will be generated according to the sponsor's standard reporting standards, including:

- Summary of ADA and NAb analysis by sample;
- Summary of ADA and NAb analysis by subject;
- Summary of incidence of ADA and NAb by dose level and cohort and study day;
- Individual plots of PK concentration against time by dose level and cohort, ADA or NAb positive subjects will be denoted by a different color or symbol versus the ADA or NAb negative subjects;
- Individual plots of PD endpoints (as defined in [Section 3.2.3](#)) against time by dose level and cohort, ADA or NAb positive subjects will be denoted by a different color or symbol versus the ADA or NAb negative subjects;
- Listing of individual level ADA and Nab incidence (clinically relevant NAb will be denoted);
- Listing of individual ABR by ADA and NAb status, separated by dose cohort.

In addition to the above standard outputs, the incidence of clinically relevant NAb will be summarized similarly as ADA and NAb, where clinically relevant is defined as a) treatment emergent Nab immune response present on ≥ 2 determinations and b) loss of PD effect (return to baseline) after previous demonstration of PD effect (in that subject) for at least 2 of the PD

parameters (total TFPI, PF1+2 and peak thrombin by Thrombin Generation Assay) during active treatment period. “Return to Baseline” is defined as follows: if the observed post baseline PD measurement falls within the two-sided 95%CI band of the baseline measurement after previous demonstration of PD effect (in that subject), then it is said that the PD measurement returns to baseline.

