- One sample will be drawn prior to IP administration for both the subcutaneous (SC) and intravenous (IV) routes of administration. For IV administration only, collect a second sample from the arm not used for IV IP administration immediately (0 to 5 minutes) following completion of the IV infusion and line flush.
- Treatment assignment may occur at any time prior to dosing once subject has met all eligibility criteria.
- IP is administered at these visits for cohorts with SC administration only.

- j. Subject diary dispensed and/or collected. Subject diary is reviewed, including information about study compliance bleeding assessments (including site and traumatic/spontaneous) and injection site reactions. At Day 1, subjects will be provided training with respect to filling out the diary including timing and nature of information to be entered.
- k. FVIII and FIX inhibitor levels must be determined by a local laboratory. A positive inhibitor test result will be above the upper limit of normal for the assay. Inhibitor test results from up to 6 months prior to Day 1 may be used to meet this requirement.

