### **9.1. Sample Size Determination**

The total sample size of approximately 24 subjects for 4 dose cohorts is based on clinical considerations to provide adequate safety, tolerability, PK, PD and efficacy information at each dose level and/or route of administration. Each single dose cohort includes 6 subjects to ensure sufficient sample size for assessment of safety, PK, PD and efficacy. Additional subjects and/or cohorts may be added to fully explore the dose range and efficacy.

This sample size is also considered sufficient to support initial analyses for efficacy based on the endpoint of annualized bleeding rate (ABR). With 6 subjects per cohort, there is greater than 80% power to detect an 85% reduction in ABR compared to a historical factor-replacement treatment (control group) at one-sided alpha of 0.1. The power calculation is based on a Poisson regression model with assumptions that the historical control group has a bleeding rate of 2.36/patient-month and the study duration is 3 months.

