3.2.3. Pharmacodynamics

- *Total TFPI; Day 1 up to Day 113.*
- *Thrombin generation (including lag time, peak thrombin generation and endogenous thrombin generation potential); Day 1 up to Day 113.*
- *Prothrombin fragment 1+2 (PF1+2); Day 1 up to Day 113.*
- *D-dimer; Day 1 up to Day 113.*
- *Dilute prothrombin time (dPT); Day 1 up to Day 113.*

Baseline will be defined as the last measurement prior to dosing on Day 1.

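### The return-to-baseline test behind the clinically relevant NAb flag judges one subject's value against a two-sided 95% CI band, which does not describe single values and counts some clear losses of effect as not returned

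*SAP*

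**What the plan says.** SAP 6.5.7.1 adds an incidence summary of clinically relevant NAb to the standard immunogenicity outputs and marks these cases in the individual listing. A case must meet two conditions:

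- **Antibody:** "treatment emergent Nab immune response present on ≥ 2 determinations".
- **Loss of PD effect:** two or more of three markers must go back to baseline in someone who had earlier shown an effect. The SAP gives the markers and the window as "parameters (total TFPI, PF1+2 and peak thrombin by Thrombin Generation Assay) during active treatment period".

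A marker has returned if the observed value "falls within the two-sided 95%CI band of the baseline measurement after previous demonstration of PD effect".

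On the PD baseline, SAP 3.2.3 says: "Baseline will be defined as the last measurement prior to dosing on Day 1". The footnote to Protocol Table 1 for the Day 1 PK and PD samples says: "One sample will be drawn prior to IP administration for both the subcutaneous (SC) and intravenous (IV) routes of administration". The second Day 1 sample in IV cohorts is taken after the infusion. Neither Table 1 nor Protocol 6.1 schedules TFPI, thrombin generation or PF1+2 at Screening.

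The SAP does not say whether the band belongs to a subject, a cohort or the whole study. It also leaves open n, scale, variance, whether the band is for a mean or for individual values, whether one later sample is enough, and whether the two parameters must return at the same visit.

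**The concern.** The rule compares a single observation with an interval named as a confidence interval. With one baseline value per subject there is no within-subject variance at baseline, so a subject's own CI cannot be formed from the baseline data alone. The CI that these data literally yield is that of a group mean. That interval measures how well the mean is known. A subject whose PD effect has gone completely has a value spread like any single baseline value, and will often lie outside it. Adding subjects narrows the interval and makes the rule less sensitive.

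The second fault does not depend on how the band is read. A value beyond baseline, on the side opposite to the drug effect, shows loss of effect at least as clearly as a value at baseline. A two-sided band calls it not returned.

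At stake is whether a low reported incidence of clinically relevant NAb can be believed. SAP 6.5.7.1 holds the only definition of that term.

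**Working it through.** The documents state no sensitivity or miss rate for this rule, so there is no planned figure to reproduce.

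**Inputs**
- Two-sided 95% band; at least 2 of 3 parameters (SAP 6.5.7.1).
- One baseline value per subject (SAP 3.2.3; Protocol Table 1).
- n = 6 per cohort (Protocol 9.1: "Each single dose cohort includes 6 subjects to ensure sufficient sample size for assessment of safety, PK, PD and efficacy") or about 24 in total (Protocol 3.1).
- Assumed: normal values on the analysis scale; a fully lost effect gives a new independent draw from the baseline distribution; independent parameters; one later sample.

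**Reading A: CI of the mean baseline**

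The band is mean ± t(0.975, n−1) × SD/√n. A new value differs from the mean with variance SD² × (1 + 1/n), so the chance of falling inside is

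p = P(|T(n−1)| < t(0.975, n−1)/√(n+1)).

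The miss under 2-of-3 is 1 − [3p²(1−p) + p³].

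| | n = 6 | n = 24 |
|---|---|---|
| t(0.975, n−1) | 2.571 | 2.069 |
| Half-width in SDs, t/√n | 1.05 | 0.42 |
| t/√(n+1) | 0.972 | 0.414 |
| p, inside the band | 62.4% | 31.7% |
| Missed, one parameter | 37.6% | 68.3% |
| Missed, 2-of-3 | 31.8% | 76.2% |

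By symmetry, half of each per-parameter miss lies on the far side of baseline: 18.8% (n=6) and about 34.15% (n=24). Making the band one-sided and changing nothing else would leave a per-parameter miss q of that size. The 2-of-3 miss, 3q²(1−q) + q³, would then be:
- n=6: 3 × 0.188² × 0.812 + 0.188³ = 0.093
- n=24: 3 × 0.3415² × 0.6585 + 0.3415³ = 0.270

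Sidedness is thus a large part of the problem under this reading, but not all of it.

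**Varying the assumptions (simulation)**

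Parameter correlation ran from 0 to 0.9 and within-subject correlation (ICC) from 0 to 0.8. For repeated samples, both visit rules were tried: the parameters must return at the same visit, or each may return at any visit.

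| Later samples that may qualify | Missed, n = 6 | Missed, n = 24 |
|---|---|---|
| 1 | 24%-36% | 68%-77% |
| 2 | 7%-17% | 45%-60% |
| 4 | 1%-9% | 13%-43% |

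**Reading B: a range for individual values**
- Mean ± 1.96 SD: missed per parameter 12.9% (n=6) or 6.7% (n=24); under 2-of-3, 4.6% or 1.3%.
- Two-sided 95% prediction interval: 5% per parameter; under 2-of-3, 3 × 0.05² × 0.95 + 0.05³ = 0.7%.

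**Proposed rule: near limit of a 95% prediction interval, one-sided**
- Per parameter: 2.5%.
- Under 2-of-3: 3 × 0.025² × 0.975 + 0.025³ = 0.0018, about 0.2% if independent.

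**The case against.** A reader might infer that the SAP rule as such misses a third to three quarters of subjects with full loss of effect. The documents do not support that, for three reasons.

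- **Type of interval.** The SAP names no mean, cohort or n. A band for individual values is just as computable from the group's baseline data, and a within-subject variance might be obtained from the planned repeated-measures model (SAP 5.2.4). The CI of a group mean is the literal reading of the wording, but not the only one possible.
- **Number of samples.** The upper figures assume one later sample. The antibody condition needs two positive determinations, and every NAb visit (Days 15, 29, 57, 85 and 113) also has PD sampling. Many qualifying subjects will have two or more relevant PD samples. Not all will: if the second positive is at Day 85 and PD loss is judged from then on, one sample remains within the treatment visits.
- **Pooling.** The 76% needs all 24 subjects in one band, while SAP 6.2.3 summarises PD by dose level and cohort.

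A reader might also infer that the immunogenicity endpoint is compromised. It is not. The secondary endpoint is the frequency of ADA and NAb (Protocol 2.2.2; SAP 3.2.4), which this flag does not alter. Individual PD plots marked by antibody status and the listing of individual ABR by ADA and NAb status keep each affected subject visible. No stopping rule or hypothesis test uses the flag.

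These objections make the numbers conditional and limit the consequence. They do not rescue the wording: a CI is the wrong interval for one observation, and the far-side misclassification remains under every reading, though it is small when the band is wide.

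**Conclusion.** The concern holds in conditional form. SAP 6.5.7.1 states a rule that, taken literally, gives wrong answers for individual subjects, and its two-sidedness is wrong however the band is read.

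The size depends on what the SAP leaves unsaid. Read as the CI of the mean baseline with one later sample, the 2-of-3 rule misses about 32% (n=6) to 76% (n=24) of full losses, assuming normal, independent parameters. If any of two to four samples may qualify, the range is about 1%-17% (n=6) or 13%-60% (n=24). If a range for individual values was intended, it is about 1%-5%. None of these figures can be called the error rate of the plan.

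The consequence is limited to the supplementary incidence table and listing flag for clinically relevant NAb. This should be changed, but it does not threaten the main analyses.

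**What to change.** Replace the definition in SAP 6.5.7.1 with a one-sided rule: a parameter has returned to baseline when the post-dose value is at or beyond the near limit (the limit on the drug-effect side) of a 95% prediction interval for a single measurement. Either form would serve:

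- baseline mean ± t(0.975, n−1) × SD × √(1 + 1/n) on the log scale, naming the group and n; or
- the subject's own baseline ± 1.96 × √2 × within-subject SD, naming the source of that SD.

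Also state the direction of drug effect for each of the three parameters, whether one sample is enough, whether the two parameters must return at the same visit, and which visits count.

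The cost is SAP wording only; no new data are needed. The downside is that a wider limit may flag some NAb-positive subjects who keep partial effect. With a cohort of 6 the limit is 2.571 × √(7/6) = 2.78 SD from the mean, against 2.069 × √(25/24) = 2.11 SD with 24 subjects pooled, so the choice of group matters. How many subjects this would affect cannot be sized, because the documents give no PD standard deviation or effect size. Requiring two NAb determinations does not reduce such flags among subjects who already meet that condition.

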7. INTERIM ANALYSES

Cumulative data will be reviewed for dose escalation as defined in Protocol Section 3.2. The safety, PK, PD and efficacy data will be routinely reviewed by the study team for internal decisions regarding future study planning. Additional cohort(s) may be added, and a cohort may be expanded to fully explore the dose range and/or efficacy endpoint following the review of the cumulative data.

No formal interim analysis will be conducted for this study. However, as this is a Sponsor-open study, the Sponsor may conduct unblinded reviews of the data during the course of the study for the purpose of safety assessment, facilitating dose-escalation decisions, facilitating PK/PD modeling, and/or to support clinical development.

9. APPENDICES

Appendix 1. Categorical Classes for ECG and Vital Signs of Potential Clinical Concern

Categories for QTcF

QTcF (ms)	$450 \leq \text{max.} < 480$	$480 \leq \text{max.} < 500$	$\text{max.} \geq 500$
QTcF (ms) increase from baseline	$30 \leq \text{max.} < 60$	$\text{max.} \geq 60$	

Categories for PR and QRS

PR (ms)	$\text{max.} \geq 300$	
PR (ms) increase from baseline	Baseline > 200 and max.	Baseline ≤ 200 and $\text{max.} \geq 50\%$ increase
QRS (ms)	$\text{max.} \geq 140$	
QRS (ms) increase from baseline	$\geq 50\%$ increase	

Categories for Vital Signs

Systolic BP (mm Hg)	$\text{min.} < 90$	
Systolic BP (mm Hg) change from baseline	$\text{max. decrease} \geq 30$	$\text{max. increase} \geq 30$
Diastolic BP (mm Hg)	$\text{min.} < 50$	
Diastolic BP (mm Hg) change from baseline	$\text{max. decrease} \geq 20$	$\text{max. increase} \geq 20$
Supine pulse rate (bpm)	$\text{min.} < 40$	$\text{max.} > 120$
Standing pulse rate (bpm)	$\text{min.} < 40$	$\text{max.} > 140$

Measurements that fulfill these criteria are to be listed in report.

Appendix 2. Clinically Significant Laboratory, Vital Sign, and ECG Values

Hematology

Hemoglobin	<0.8 times the LLN or <80% times the baseline value if the baseline result is less than the lower limit of the reference range
Hematocrit	<0.8 times the LLN or <80% times the baseline value if the baseline result is less than the lower limit of the reference range
Platelets	<100,000 or ≤ 0.77 times the baseline value if the baseline result is less than the lower limit of the reference range.

Chemistry

Total bilirubin:	>1.5 times the ULN
Direct bilirubin:	>1.5 times the ULN
Indirect bilirubin:	>1.5 times the ULN
Creatinine kinase:	>2.0 times the ULN
Creatinine:	>1.3 times the ULN

Coagulation Pathway

PT:	≥ 4 seconds above the limits of the reference range
Cardiac Troponin I:	If values are normal at baseline, any results above the myocardial ischemia range Any result in the myocardial infarction range, regardless of baseline values
Fibrinogen:	≤ 0.5 times LLN or ≤ 0.5 times the baseline value

Vital Signs

Temperature:	>38.5°C
Pulse Rate	
Supine/Sitting:	<40 or >120 BPM
Standing:	<40 or >140 BPM
Blood Pressure:	Systolic ≥ 30 mm Hg change from baseline in same posture
<90 mm Hg	Systolic

Diastolic: ≥ 20 mm Hg change from baseline in same posture Diastolic < 50 mm Hg

Electrocardiogram

PR interval ≥ 300 msec

≥ 1.25 times baseline when baseline > 200 msec

≥ 1.50 times baseline when baseline ≤ 200 msec

QRS interval ≥ 140 msec

≥ 1.50 times baseline

QTcF interval ≥ 500 msec
